## **Precision**

The precision refers to the level of sampling error. The standard error and consequently the width of confidence intervals (CI) are measures of precision. As the VE CIs are asymmetric, we express precision as the lower limit of the two-sided CI of the anticipated true VE, expressed in %. The precision can be derived starting from the anticipated true VE, the confidence coefficient  $(1 - \alpha/2)$ , the number of cases, the 'cases to controls' ratio 1:*r* and the overall vaccination coverage  $\gamma$ . Consider the notation as defined in Table 1, where *N* is the total number of subjects,  $N_d^+$  the number of cases,  $N_d^-$  the number of controls,  $N_e^+$  the number of vaccinated subjects,  $N_e^-$  the number of unvaccinated subjects and where *r* is the number of controls per case and  $\gamma$  is the coverage.

Table 1: Cross-tabulation of	f exposure a	and disease in a	case-control study
------------------------------	--------------	------------------	--------------------

	Diseased				
		Yes (cases)	No (controls)		
Exposed	Yes	a	b	$N_e^+ = N \gamma$	
	No	С	d	$N_e^- = N(1 - \gamma)$	
		$N_d^+$	$N_d^- = r N_d^+$	N	

Then, from the lower limit of the CI for VE estimates based on a case-control study, or

$$VE_{LL CI} = 1 - exp \left[ \log(OR) + Z_{\alpha/2} \sqrt{\frac{1}{a} + \frac{1}{b} + \frac{1}{c} + \frac{1}{d}} \right],$$
(3)

where OR = 1 - VE and where  $Z_{\alpha/2}$  is the standard normal z-score, it follows that the precision is determined for given values for *a*, *b*, *c* and *d*. From anticipated values for *OR*,  $N_e^+$ ,  $N_e^-$  and  $N_d^+$ , the

cell count a can be analytically derived as;

$$a = \left(\frac{1}{2}\right) \sqrt{\frac{x_1 + x_2 + x_3}{(OR - 1)^2}} + \frac{N_e^+ OR + N_e^- + N_d^+ OR - N_d^+}{2(OR - 1)},$$
  

$$b = N_e^+ - a$$
  

$$c = N_d^+ - a$$
  

$$d = N_d^- - b$$

where  $x_{1} = N_{e}^{+2} OR^{2} + 2N_{e}^{+}N_{e}^{-}OR - 2N_{e}^{+}N_{d}^{+}OR^{2} + 2N_{e}^{+}N_{d}^{+}OR$   $x_{2} = N_{e}^{-2} + 2N_{e}^{-}N_{d}^{+}OR - 2N_{e}^{-}N_{d}^{+}$   $x_{3} = N_{d}^{+2}OR^{2} - 2N_{d}^{+2}OR + N_{d}^{+2}$ 

We calculated the precision of the overall VE based on a two-sided 95% CI for case-control studies using 'cases to controls' ratio of 1:1, 1:2 and 1:4 with the total number of cases varying from 100 to 4000, while assuming overall vaccination coverages of 5%, 20%, 50% and 70% and overall VE of 20%, 50% and 70%.

We additionally calculated the precision of the brand-specific VE, where cases/controls are considered exposed when they were vaccinated with the brand of interest and unexposed when they were unvaccinated. This means that subjects vaccinated with another brand are excluded from the analysis and that the same comparator group of unexposed subjects is used for the different brand-specific estimates. The precision of brand-specific VE is calculated for case-control studies using a 'cases to controls' ratio of 1:1 using the same settings as above, additionally assuming that the brand of interest accounts for 10%, 20%, 40%, 60%, 80% and 90% of the overall vaccination coverage.

The results for precision of the overall VE using 'cases to controls' ratio of 1:1, 1:2 and 1:4 are given in Figure 3 to 5, respectively. These figures represent precision by number of cases. The results for the precision of brand-specific VE using 'cases to controls' ratio of 1:1 for anticipated true VE of 20%, 50% and 70% are given in Figures 6 to 8.

c) 70% VE

**Figure 3.** Precision of overall VE for a case-control study (1:1 case-control ratio) assuming overall vaccination coverage of 5%, 20%, 50% and 70%, and anticipated true VE of 20%, 50% and 70% (indicated with the black horizontal line), by number of cases.

c) 70% VE

**Figure 4.** Precision of overall VE for a case-control study (1:2 case-control ratio) assuming overall vaccination coverage of 5%, 20%, 50% and 70%, and anticipated true VE of 20%, 50% and 70% (indicated with the black horizontal line), by number of cases.

c) 70% VE

**Figure 5.** Precision of overall VE for a case-control study (1:4 case-control ratio) assuming overall vaccination coverage of 5%, 20%, 50% and 70%, and anticipated true VE of 20%, 50% and 70% (indicated with the black horizontal line), by number of cases.

**Figure 6.** Precision of brand-specific VE for a case-control study (1:1 cases to controls ratio) assuming an anticipated true VE of 20% (indicated with the black horizontal line), overall vaccination coverage of 5%, 20%, 50% and 70% with the brand of interest covering 10%, 20%, 40%, 60%, 80% and 90% of the overall coverage, by number of cases.

**Figure 7.** Precision of brand-specific VE for a case-control study (1:1 cases to controls ratio) assuming an anticipated true VE of 50% (indicated with the black horizontal line), overall vaccination coverage of 5%, 20%, 50% and 70% with the brand of interest covering 10%, 20%, 40%, 60%, 80% and 90% of the overall coverage, by number of cases.

**Figure 8.** Precision of brand-specific VE for a case-control study (1:1 cases to controls ratio) assuming an anticipated true VE of 70% (indicated with the black horizontal line), overall vaccination coverage of 5%, 20%, 50% and 70% with the brand of interest covering 10%, 20%, 40%, 60%, 80% and 90% of the overall coverage, by number of cases.

## **Concluding remarks and recommendations**

We make the following observations and recommendations based on our sample size calculations for single-site case-control studies;

- We recommend case-control studies based on 500 cases or more. A case-control study with 500 cases and a 1:1 'case to control' ratio will result in 95% CIs of the overall VE with a lower limit of >30% given a true VE of 50% and an influenza attack rate of 5%, for coverages of > 20%.
- Case to control ratios of 1:2 or 1:4 yield slightly more accurate estimates compared to a 1:1 case to control ratio.
- A case-control study with 500 cases and a 1:1 'case to control' ratio will result in 95% CIs of the brand-specific VE with a lower limit of >25% given a true VE of 50% for brands covering 40% to 90% of the influenza vaccines when the overall vaccination coverage is 50% or more.
- A case-control study with 500 cases and a 1:1 'case to control' ratio will result in a minimal detectable overall VE of 30-40% for coverages >20%.
- A case-control study based on 500 cases and a 1:1 'case to control' ratio will result in minimal detectable brand-specific VE of 30-40%, for brands covering 40% to 90% of the influenza vaccines when the overall vaccination coverage is 50% or more.
- A case-control studies based on 1500 to 2000 cases and a 1:1 case to control ratio will result in a minimal detectable VE of 18-20% for an overall vaccination coverage of 20% or more. Improvements in accuracy both in terms of minimal detectable VE and precision will be minimal when increasing sample sizes further
- In case the VE is expected to be low (< 20%), higher sample sizes are required to obtain VE estimates with acceptable precision.
- In case interest is in VE within subgroups, the sample size calculations should be done with respect to the subgroup-specific sample size.
- IMPORTANT: These are recommendations to support the design of case-control studies on (brand-specific) VE. Obtaining a minimum sample size is not a requirement for study participation.

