## Sample size considerations

This section gives sample size considerations and formulates recommendations. These recommendations are meant to support the design of the case-control studies on IVE. Obtaining a minimum sample size is not a requirement for study participation. Details on the sample size calculations based on the minimal detectable VE as well as precision are given in Annex 3.

DRIVE recommends case-control studies based on 500 cases or more. However, studies with smaller sample sizes might still contribute to the power of the pooled analyses, provided that the study site is able to optimally harmonise its protocol with the other study sites to minimize the

between-study heterogeneity. In case VE estimates with unacceptable large CIs are obtained, it might be considered to not report these estimates.

Figure 1 presents the precision of the overall VE for number of cases varying from 200 to 4000 subjects, when assuming a true VE of 50%, a 'cases to controls' ratio of 1:1 and a total vaccination coverage of 5%, 20%, 50% and 70%. The number of cases per control is likely to vary (by definition of test-negative design). The calculations are based on an anticipated true VE of 50% as this is a conservative choice, requiring larger sample sizes compared to assuming lower/higher VE values. A case-control study based on 500 cases and a 1:1 'cases to controls' ratio will result in 95% CIs of the overall VE with a lower limit larger than 30% given a true VE of 50%, for coverages of >20%.

**Figure 1.** Precision of the overall VE expressed as the lower limit of the 95% CI, assuming a true VE of 50%, a 'cases to controls' ratio of 1:1 and a total vaccination coverage of 5%, 20%, 50% and 70%.

Figure 2 presents the precision of the brand-specific VE for number of cases varying from 200 to 4000 for the same parameter settings as above and additionally assuming the brand of interest accounts for 10%, 20%, 40%, 60%, 80% and 90% of the total vaccination coverage. A case-control study based on 500 cases and a 1:1 'cases to controls' ratio will result in 95% CIs of the brand-specific VE with a lower limit larger than 25% given a true VE of 50%, for brands covering 40% to 90% of the influenza vaccines when the overall vaccination coverage is 50% or more.

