## Minimal detectable vaccine effectiveness

The minimal detectable VE is the smallest VE that can be detected as significantly greater than zero in a given study using hypothesis testing. The minimal detectable VE for a case-control study is estimated as

$$VE_{MD} = 1 - RR_{MD(RR<1)},\tag{1}$$

where  $RR_{MD(RR<1)}$  is the minimal detectable relative risk (RR) if RR < 1, or

$$RR_{MD(RR<1)} \cong 1 + \frac{-b - \sqrt{b^2 - 4a(r+1)}}{2a},$$
 (2)

where

$$a = r\gamma^2 - \frac{Nr\gamma(1-\gamma)}{\left(\frac{z_{\alpha}}{2} + z_{\beta}\right)^2 (r+1)} \quad ; b = 1 + 2r\gamma,$$

for 'cases to controls' ratio *r*, coverage  $\gamma$ , total number of subjects *N*, and where  $z_{\alpha}$  and  $z_{\beta}$  are the standard normal z-scores for the type I and type II error rates (Woodward 2013).

We calculated the minimal detectable overall VE (1) with 80% power  $(1 - \beta)$  and a two-sided 95% confidence coefficient  $(1 - \alpha/2)$  for case-control studies using 'cases to controls' ratio of 1:1, 1:2 and 1:4 with the number of cases varying from 100 to 4000, while assuming overall vaccination coverages of 5%, 20%, 50% and 70%.

We additionally calculated the minimal detectable brand-specific VE, where cases/controls are considered exposed when they were vaccinated with the brand of interest and unexposed when they were unvaccinated. This means that subjects vaccinated with another brand are excluded from the analysis and that the same comparator group of unexposed subjects is used for the different brand-specific estimates. The minimal detectable brand-specific VE is calculated for the same settings above, additionally assuming that the brand of interest accounts for 10%, 20%, 40%, 60%, 80% and 90% of the overall vaccination coverage.

The results for the minimal detectable overall VE for the 1:1, 1:2 and 1:4 'cases to controls' ratios are given in Figure 1. These figures represent the minimal detectable VE by number of cases. The results for the minimal detectable brand-specific VE for the 1:1 'cases to controls' ratio and assuming overall vaccination coverages of 5%, 20%, 50% and 70% are given in Figure 2.

c) 1:4 cases to controls

**Figure 1.** Minimal detectable overall vaccine effectiveness for a case-control study (1:1, 1:2 and 1:4 cases to controls ratio) assuming vaccination coverage of 5%, 20%, 50% and 70% by number of cases.

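### Annex 3's minimal detectable VE of 18-20% with 1500-2000 cases does not hold at 20% coverage, where its own formula gives 20.5-23.4%

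*Combined protocol and SAP*

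**What the plan says.** Annex 3, under Minimal detectable vaccine effectiveness, defines the quantity: "The minimal detectable VE is the smallest VE that can be detected as significantly greater than zero in a given study using hypothesis testing". It sets the operating characteristics ("We calculated the minimal detectable overall VE (1) with 80% power" and "a two-sided 95% confidence coefficient"), gives equation (2) for the RR<1 case, and applies it at coverages of 5%, 20%, 50% and 70%.

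Under Concluding remarks and recommendations it then states that a study with between 1500 and 2000 cases, and one control for each, "will result in a minimal detectable VE of 18-20% for an overall vaccination coverage of 20% or more". The same bullet adds: "Improvements in accuracy both in terms of minimal detectable VE and precision will be minimal when increasing sample sizes further". The next bullet says that larger samples are needed when VE is expected to be below 20%.

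The main protocol's Sample size considerations section refers to Annex 3 for details and describes the recommendations as support for study design. Both places say that a minimum sample size is not a condition of participation.

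**The concern.** Minimal detectable VE depends strongly on coverage, and 20% coverage is the least favourable point of the annex's grid that the bullet includes. A single narrow range for every coverage from 20% upwards, and for both 1500 and 2000 cases, is therefore doubtful on its face. A site with about 20% coverage that relied on the bullet would believe it had 80% power for a VE of 18-20% when it did not. The remark about diminishing returns could also discourage recruitment that would help such a site.

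**Working it through.** **Inputs.** From Annex 3: two-sided 5% (z = 1.960), 80% power (z = 0.842), r = 1, N = 2 × cases, and coverage γ of 20%, 50% and 70%. The squared sum of the z-scores is 7.849.

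**Formula (equations 1 and 2, RR<1 root).**
- a = rγ² − N r γ(1−γ) / [7.849 (r+1)]
- b = 1 + 2rγ
- RR = 1 + [−b + √(b² − 4a(r+1))] / (2a)
- VE = 1 − RR

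**Step 1: reproduce a stated figure.** For 500 cases and γ = 0.20:
- a = 0.04 − 160/15.698 = −10.153 and b = 1.4
- √(1.96 + 81.22) = 9.120
- RR = 1 + 7.720/(−20.306) = 0.620, so VE = 38.0%

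At 50% and 70% coverage the results are 29.9% and 31.2%. These agree with the annex's 30-40% for 500 cases, so the formula and inputs are the ones the authors used.

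**Step 2: the disputed bullet at 20% coverage.**
- 1500 cases: a = 0.04 − 480/15.698 = −30.538; √(1.96 + 244.30) = 15.693; RR = 1 + 14.293/(−61.076) = 0.766; VE = 23.4%.
- 2000 cases: a = 0.04 − 640/15.698 = −40.730; √(1.96 + 325.84) = 18.105; RR = 1 + 16.705/(−81.460) = 0.795; VE = 20.5%.

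| Cases | 20% coverage | 50% | 70% |
|---|---|---|---|
| 1500 | 23.4% | 18.5% | 19.6% |
| 2000 | 20.5% | 16.2% | 17.3% |

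The range over the annex's own grid is 16.2-23.4%. Only 1500 cases at 50-70% coverage falls within 18-20%. With 1500 cases the result is 20% or lower only for coverage between about 32.5% and 72%.

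**Step 3: what 20% coverage requires.** Solving the same equation gives about 2,110 cases for a minimal detectable VE of 20% and about 2,650 for 18%. At a true VE of 20%, power is 65.5% with 1500 cases and 77.8% with 2000.

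**Step 4: other readings.** A two-proportion power calculation with coverage taken in controls gives 23.4% and 20.5%; a Wald log-odds-ratio formula gives 23.5% and 20.5%. Taking coverage over cases and controls together gives 22.6% and 19.9%. At 20% coverage, one-sided testing gives 21.0% and 18.4%, and a 1:2 ratio gives 20.7% and 18.1%. None yields 18-20% across the stated settings.

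**Step 5: the remark on further increases, 2000 to 4000 cases.**
- Minimal detectable VE: 20.5% to 14.8% at 20% coverage (4000 cases: a = −81.50, RR = 0.852).
- Lower 95% limit by equation (3), true VE 50%, Table 1 coverage: 41.3% to 44.0% (20% coverage), 43.3% to 45.3% (50%), 42.6% to 44.9% (70%).

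**Step 6: the sign in equation (2).** Because a is negative at every setting tried, the minus sign shown before the square root gives RR>1. For 1500 cases at 20% coverage, RR = 1 + (−17.093)/(−61.076) = 1.280.

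**Step 7: the 500-case lower limit.** Table 1 defines coverage over the whole sample. With N = 1000 and γ = 0.20 the cells are a = 72.84, b = 127.16, c = 427.16, d = 372.84, with standard error 0.1631. The lower limit is 1 − 0.5 × exp(1.96 × 0.1631) = 31.2%.

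**The case against.** The strongest reply is that the consequence is small. At 2000 cases and 20% coverage the gap is half a percentage point, and it disappears (19.9%) if coverage is read over cases and controls together. The main recommendation is 500 cases and is unaffected. The annex is advisory, and small sites can still contribute to pooling. All of this stands and limits the weight of the point. It does not rescue 1500 cases at 20% coverage, which gives 22.6-23.5% on every two-sided 1:1 reading at 80% power.

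The remark on diminishing returns also has a partial defence. It covers precision as well, where doubling the sample gains only about 2-3 points at a true VE of 50% (about 3-4 points at a true VE of 20%), and the next bullet already asks for more cases when VE is low. That defence holds for precision. It does not hold for minimal detectable VE.

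Three stronger readings are tempting and are not supported:
- A reader might infer that equation (2) is wrong and the annex's figures with it. The plus root reproduces the 500-case bullet, so the calculations used the right root. The equation was also machine-read from PDF, so a misread sign cannot be excluded.
- A reader might infer that the 500-case precision claim, "with a lower limit larger than 30% given a true VE of 50%, for coverages of >20"%, fails too. It gives 28.7% at 20% coverage only if coverage is redefined as coverage in controls. Under Table 1's definition, which governs that calculation, the limit is 31.2% and the claim holds.
- A reader might cite results at 5% coverage against the remark on further increases. The bullet is confined to 20% or more.

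**Conclusion.** The 18-20% statement is wrong as written for its stated condition. By the annex's own equation, the minimal detectable VE with 1500-2000 cases is 20.5-23.4% at 20% coverage and 16.2-19.6% at 50-70%. The error is optimistic at 20% coverage and slightly pessimistic for 2000 cases at 50-70% coverage. The clear failure is 1500 cases at 20% coverage; the shortfall with 2000 is marginal. The remark that further increases bring little is unsupported for minimal detectable VE.

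This rests on 80% power, a two-sided 5% level, a 1:1 ratio, the RR<1 root, and coverage entered in equation (2) as γ. It affects planning at sites with coverage near 20%. No analysis or reported estimate depends on it.

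**What to change.** In Annex 3, Concluding remarks and recommendations:

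1. Restate the bullet as: 1500-2000 cases at 1:1 give a minimal detectable VE of about 16-20% at 50-70% coverage and about 20.5-23.4% at 20% coverage. Optionally add that 20% at 20% coverage needs about 2,110 cases.
2. Limit the sentence on minimal further improvement to precision, preferably naming the true VE of 50% at which it is a fair description.
3. Check the sign before the square root in equation (2) against the source, and correct it if it is printed as shown.
4. Leave the 500-case statement on the lower limit above 30% unchanged.

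The cost is a few lines of annex wording. The figure becomes less favourable at 20% coverage and slightly more favourable for 2000 cases at 50-70%. No design or analysis changes.

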Annex 4: Generic Statistical Analysis Plan for pooled analysis

DRIVE D4.4 Generic Statistical Analysis Plan: combining information on Influenza Vaccine Effectiveness across study sites

# **Document History**

Version	Date	Description		
	07 11 2017	Outline - first draft		
V1.0	29 01 2018	First draft		
	22 02 2018	Comments [name] and [name]		
V1.1 26 02 2018 Second draft		Second draft		
	09 03 2018	Comments WP4 team members		
V1.2 12 03 2018 First version, to		First version, to share with SC		
	26.03.2018	Comments SC: Seqirus, SP, GSK, IRD, THL		
V1.3	29.03.2018	Final version		
	18.04.2018	Addition of paragraph about sample size considerations and requirements following discussion with SC		

#### LIST OF ABBREVIATIONS

- AD-MA Aggregated data meta-analysis
- CI Confidence interval
- DRIVE Development of Robust and Innovative Vaccine Effectiveness
- IPD-MA individual participant data meta-analysis
- IVE Influenza vaccine effectiveness
- OR Odds ratio
- RR Relative risk
- SAP Statistical Analysis Plan
- RRR Relative Risk Ratio

# BACKGROUND

The DRIVE consortium aims to enable the collaboration of different public and private stakeholders to perform annual brand-specific influenza vaccine effectiveness (IVE) studies for various influenza vaccines on the European market. To this end, IVE studies will be conducted at various study sites across Europe. In a second step, the site-specific data will be combined to obtain overall estimates at the European level. The purpose of this document is to provide guidance for writing the Statistical Analysis Plan (SAP) of combining and presenting information on IVE from different study sites. This document will be updated following the learnings from the pilot year 2017-2018.

There are two statistical approaches for pooling data: a one-stage or a two-stage pooling approach (1). The two-stage approach refers to the classical meta-analytical approach, also called aggregated data meta-analysis (AD-MA). In this approach, the patient-level or minimally aggregated data from each study are analysed separately in order to obtain the effect estimates of interest (here vaccine effectiveness estimates) and the corresponding confidence intervals (CIs). Then, in the second step, the effect estimates are combined by an appropriate meta-analysis model to obtain the meta-analytical (weighted averaged) estimate. The one-stage pooling approach analyses all the combined patient-level or minimally aggregated data from the different data sources in a single step. This approach is also called the individual participant data meta-analysis (IPD-MA).

We opt to pool data using the AD-MA approach, given the statistical equivalence of AD-MA and IPD-MA, given that many of the mentioned advantages of IPD-MA (i.e. transforming data to common sources or measures and standardizing analysis) can also be achieved through harmonization/standardization of the individual site-specific studies and given the additional complexity of performing IPD-MA when data are collected using different study designs (1). Within AD-MA, we prefer the use of random effects meta-analysis model, which assumes that the observed effect estimates can vary across study sites because of differences in the treatment effect in each study site (e.g. due to differences in population, in health care utilization, in circulating influenza strains) as well as sampling variability.

This document builds further upon or relates to the DRIVE generic study protocols for the analyses and presentation of data collected at a single study site, the DRIVE data management plan and the DRIVE report template (see Reference documents).

# **REFERENCE DOCUMENTS**

[Here: refer to the generic study protocols for the analyses of the study site-specific data, the data management plan and the report template]

# AGGREGATED DATA META-ANALYSIS

## **Objective(s)**

To estimate seasonal IVE (%) through pooling site-specific estimates obtained as described in the site-specific protocols.

[Describe the primary and secondary objectives as per study protocol mentioned in Section 2 and for which pooling will be performed]

